### **6.3. Appendix 3: Clinical Trial Registry Analyses**

Additional analyses will be performed for the purpose of fulfilling the Clinical Trial Registry (CTR) requirements.

Analyses provided for the CTR requirements include the following:

- Summary of adverse events, provided as a dataset which will be converted to an XML file. Both Serious Adverse Events and ‘Other’ Non-Serious Adverse Events are summarized: by treatment group, by MedDRA PT.
- An AE is considered ‘Serious’ whether or not it is a TEAE.
- An AE is considered in the ‘Other’ category if it is both a TEAE and is not serious. For each Serious AE and ‘Other’ AE, for each term and treatment group, the following are provided:
  - the number of participants at risk of an event
  - the number of participants who experienced each event term
  - the number of events experienced.
- For each Serious AE, these additional terms are provided for European Union Drug Regulating Authorities Clinical Trials (EudraCT):
  - the total number of occurrences causally related to treatment
  - the total number of deaths
  - the total number of deaths causally related to treatment.
- Consistent with [www.ClinicalTrials.gov](http://www.ClinicalTrials.gov) requirements, ‘Other’ AEs that occur in fewer than 5% of patients/subjects in every treatment group may be excluded if a 5% threshold is chosen. Allowable thresholds include 0% (all events), 1%, 2%, 3%, 4%, and 5%.
- AE reporting is consistent with other document disclosures for example, the clinical study report (CSR), manuscripts, and so forth.
- Demographic table including the following age ranges required by EudraCT: in utero, preterm newborn infants (gestational age <37 weeks), newborns (0-27 days), infants and toddlers (28 days – 23 months), children (2-11 years), adolescents (12-27 years), adults (18-64 years), 65-85 years, and 85 years and over.

### **6.4. Appendix 4: Concomitant Therapy**

Concomitant therapy is defined as the therapy that starts before, on, or after the first day of study treatment and before the last dose date in the treatment period, and continues into the treatment period, that is, either no end date (the therapy is ongoing) or an end date on or after the first day of study treatment.

The number and percentages of participants who take concomitant medication will be summarized by treatment using PTs nested within Anatomical Therapeutic Chemical (ATC) codes. The concomitant medications will be ordered by decreasing frequency of LY3209590 within each ATC.

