**Intervention Groups and Duration:**

Participants who meet entry criteria will be randomly assigned in a 1:1 ratio to LY3209590 or insulin glargine basal insulin treatment. LY3209590 will be administered once weekly, and insulin glargine will be administered once daily.

Participants will also be treated with insulin lispro as prandial insulin.

[figure not shown]
The study treatment period duration is 26 weeks.

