### **Insulin glargine frequency of administration**

Insulin glargine should be administered daily at approximately the same time each day.

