### **Study participants treated with LY3209590**

Participants will administer their last dose of LY3209590 at Week 25 of the study and can begin the transition to the non-study insulin after Visit 23 (Week 26). At Visit 23 (Week 26), the investigator will review instructions for transitioning to the non-study insulin with the participant. The non-study daily basal insulin treatment should be started slowly and under regular review of glucose profiles after discontinuation of LY3209590.

Since LY3209590 has a half-life of approximately 17 days, a slow up-titration of the non-study daily basal insulin is necessary to prevent hypoglycemia due to overlapping insulin action. Non-study basal insulin would not be required until the study participant's fasting glucose is above 120 mg/dL (6.6 mmol/L), and then daily basal insulin would be initiated and adjusted based on fasting glucose, other SMBGs, hypoglycemia evaluation, and other clinical factors. The investigator should consider titration of the non-study basal insulin to reach 50% of the required daily basal insulin dose at approximately 2 weeks and 80% of the required daily basal insulin dose at approximately 4 weeks. In addition to Visit 801, unscheduled visits may occur during this time to facilitate the transition to non-study daily basal insulin.

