### **Study participants treated with insulin glargine**

Participants assigned to the insulin glargine treatment arm will transition to their non-study basal insulin after Visit 23 (Week 26) with dose adjustment per investigator discretion based on fasting glucose, other SMBGs, and hypoglycemia evaluation and in accordance with the local product label for the basal insulin.

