### 4.6.1. Extent of Exposure

Duration of exposure to study treatment will be summarized. No p-values will be reported in these tables as they are intended to describe the study populations, rather than test hypotheses about them. Total patient-years of exposure will be reported. The number and proportion of participants falling into the following different exposure categories will also be summarized by study treatment

- $>0, \geq 30$  days,  $\geq 90$  days,  $\geq 180$  days
- $>0$  and  $< 30$  days,  $\geq 30$  and  $< 90$  days,  $\geq 90$  and  $< 180$  days,  $\geq 180$  days

Exposure on study treatment will be calculated as

- LY3209590: date of the last treatment administration – date of first treatment administration + 7 days
- Insulin glargine: date of the last treatment administration – date of first treatment administration + 1 day

Total patient-years of exposure will be calculated by the sum of duration of exposure in days divided by 365.25. The following summary statistics will be provided: n, mean, standard deviation, median, minimum, maximum, interquartile range, and total exposure (that is, total patient-years).

All participants who complete the study treatment period are required to complete a safety follow-up period and participants who discontinue the study treatment prematurely are encouraged to remain in the study for safety monitoring. The duration on study from the first dose of study treatment to the study disposition date will also be summarized by treatment.

A listing of exposure to study treatment will be provided.

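### SAP Appendix 4 closes the window for new concomitant therapy 6 to 7 days earlier on LY3209590 than on glargine, which slightly distorts a descriptive by-arm table

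*SAP*

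**What the plan says.** SAP Appendix 4 (Section 6.4) defines a concomitant therapy as one that "starts before, on, or after the first day of study treatment and before the last dose date in the treatment period" and that is still ongoing or ends on or after the first treatment day. The number and percentage of participants are then summarised by arm, by preferred term within ATC code.

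The dosing calendars differ by arm:

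- LY3209590 (Protocol 6.6.1): "Participants will administer their last dose of LY3209590 at Week 25 of the study".
- Glargine (Protocol 6.1): "Insulin glargine should be administered daily at approximately the same time each day". Protocol 6.6.1 places the switch to non-study basal insulin after Visit 23 (Week 26).
- Both arms (Protocol 1.1): "The study treatment period duration is 26 weeks".

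Elsewhere the SAP allows for the different dosing intervals:

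- Exposure (Section 4.6.1) for the weekly arm is "LY3209590: date of the last treatment administration – date of first treatment administration + 7 days", against one added day for glargine.
- The EAS2 cutoff (Section 3) is 10 days after the last dose for LY3209590 and 1 day for glargine.
- The hypoglycemia treatment period (Section 4.1) ends at Visit 23 for completers in both arms.

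Appendix 4 makes no such allowance, and no other section supplies one.

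**The concern.** A rule that reads the same for both arms gives them different observation windows. A weekly insulin's last injection comes about a week before the end of treatment, and a daily insulin's comes at the end. A completer who starts, say, an antibiotic in the final week is counted if on glargine and dropped if on LY3209590, although both are still in the treatment period.

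After early stopping, an LY3209590 participant likewise loses the days still covered by the last weekly dose. What is at stake is whether the two columns of the concomitant medication table describe the same stretch of the trial.

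**Working it through.** The plan states no figure for this point, so the check is date arithmetic followed by an illustration of size.

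**Inputs.** Day 0 is the first dose. The last LY3209590 dose is at Week 25 (Protocol 6.6.1). Glargine is daily, with the switch after Visit 23 at Week 26 (Protocol 6.1 and 6.6.1). The treatment period is 26 weeks. A start date must fall strictly before the last dose date (SAP 6.4).

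**Window for new starts, on-schedule completers**

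- LY3209590: 25 × 7 = 175, so start dates up to day 174 count.
- Glargine: 26 × 7 = 182. The last dose is on day 181 or 182, depending on whether a dose is taken on the day of Visit 23, so start dates up to day 180 or 181 count.
- Gap: 181 − 175 = 6 days, or 182 − 175 = 7 days.
- Share of the period: 6/182 = 3.3%, or 7/182 = 3.8%.
- If Visit 23 moves within a ±3-day tolerance while the Week 25 dose stays fixed, the 7-day gap becomes 7 − 3 = 4 to 7 + 3 = 10 days.

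**Comparison with the SAP exposure rule.** LY3209590: 175 + 7 = 182 days. Glargine: 181 + 1 = 182 or 182 + 1 = 183 days. That rule makes the arms equal to within a day; Appendix 4 leaves them 6 to 7 days apart.

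**Illustration of size.** Assume equal true use in both arms and a constant start rate, with a proportion p first starting a given term over 182 days. The documents give no start rates, so p is varied.

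- Shown on LY3209590: 1 − (1 − p)^(175/182).
- Shown on glargine: p if the last dose is on day 182, or 1 − (1 − p)^(181/182) if on day 181.

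| p | Shown on LY3209590 | Deficit, 7-day gap (points) | Deficit, 6-day gap (points) | 7-day deficit × 335 per arm |
|---|---|---|---|---|
| 2% | 1.92% | 0.08 | 0.07 | 0.26 participants |
| 10% | 9.63% | 0.37 | 0.31 | 1.2 participants |
| 30% | 29.03% | 0.97 | 0.83 | 3.2 participants |
| 60% | 58.57% | 1.43 | 1.23 | 4.8 participants |

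The 335 per arm is 670/2 randomised, treated here as if all completed on schedule.

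**The case against.** **This is a descriptive table, and little of it moves.** That stands. No test, model or estimand is attached to the definition. Therapies already under way before the Week 25 dose count in both arms. Only a participant's first start of a given term in that final week is affected.

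**The glargine date is not in the documents.** Correct. It is inferred from daily dosing and the switch after Visit 23, so the gap is given as 6 to 7 days.

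**The last dose might mean lispro, which both arms take to Week 26.** This does not stand. The SAP's exposure and treatment-period rules are written for LY3209590 and glargine only, and the intervention table in Protocol 6.1 describes lispro as background therapy.

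**The SAP uses different cutoffs for different purposes.** True. The study-dose analysis, for example, uses the last dose date without extension, so nothing obliges Appendix 4 to copy the exposure rule. That bears on the choice of remedy, not on the asymmetry.

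**A reader might infer that drugs for adverse events or high glucose go missing from the safety picture.** The documents do not support that. Rescue therapy has its own start date in the EAS2 cutoff and its own participant listing (SAP 3 and 4.6.2). Adverse events are analysed through the last visit, including follow-up, in both arms (SAP 4.1).

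**A reader might also infer that adding 7 and 1 days, or ending inclusively at Visit 23, mends this at no cost.** It does not. Non-study insulin is prescribed at Visit 23 (Protocol 4.1 and 6.6.1), so an inclusive limit could count it as concomitant. The arms could differ here too, because the protocol defers non-study basal insulin on LY3209590 until fasting glucose rises. Participants who stop early may receive another glucose-lowering drug (Protocol 7.1). With added days of 7 and 1, one started on day 3 after the last dose would count on LY3209590 and not on glargine. The present strict cutoff at least excludes such replacements in both arms.

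**Conclusion.** The asymmetry is real and follows from the rule as written. For on-schedule completers the new-start window is 6 to 7 days (3.3% to 3.8% of 182) shorter on LY3209590, and the error always understates that arm. It is about 0.1 percentage points or less for terms started by about 2% of participants, and about 1.4 points at most for terms started by 60%. Those figures assume a constant start rate, equal true use and on-schedule dosing; the start proportions are illustrative.

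The consequence stops at the concomitant medication table. The primary and key secondary analyses, rescue and adverse event reporting, type I error and power do not depend on this definition. It is a minor correction, worth making because it is cheap and because the SAP already handles the same dosing-interval difference in three other places.

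**What to change.** - **Participants who complete treatment:** in both arms, require the start date to fall before the Visit 23 date, the endpoint that SAP 4.1 already uses for hypoglycemia in completers. Exclude non-study transition insulin prescribed at Visit 23. The between-arm gap for completers is then nil.
- **Participants who stop early:** do not simply add 7 and 1 days. Either keep the last dose date and footnote the difference, or extend the window over the last dosing interval and exclude, or flag separately, glucose-lowering therapy started to replace the study insulin.

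The cost is one extra date variable, a flag for transition or replacement insulin, and a sentence or two in Appendix 4. No new data are needed: Protocol 6.8 already collects medication start and end dates. SAP 4.1 allows such a change to be documented in the SAP or the clinical study report.

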## 6.5. Appendix 5: Protocol Deviations

IPDs are the deviations from the study protocol that may compromise the data integrity and patients' safety. The IPD category and details of IPD identification are provided in the trial issue management plan.

The number and percentage of participants with any reported IPDs will be summarized by treatment group and IPD category. The IPDs identified by site monitoring and clinical database will be integrated. If the IPD is identified by both methods, only the site monitoring IPD will be presented.

## 6.6. Appendix 6: Derivation of CGM Variables

Blinded CGM will be worn by participants at the following designated weeks:

- Two weeks in screening/lead-in period with the data download at Week 0 (Visit 3)
- Four weeks after the initiation of study treatment with the data download at Week 4 (Visit 7)
- Four weeks near the end of weekly titration period with the data download at Week 12 (Visit 15)
- Four weeks near the primary endpoint with the data download at Week 26 (Visit 23)
- Four weeks after the end of study treatment period with the data download at Week 31 (Visit 802).

Linear interpolation will be used to impute the missing glucose readings during intervals  $>7$  minutes and  $\leq 15$  minutes. Missing data will be imputed at a 5-minute interval using the BG value before and the one after the interval. For example, the BG reading before the interval is 50 mg/dL at time 100 min, and the BG reading after interval is 70 at time 115 min, then the missing records will be imputed as:

- at time 105 min, BG reading= $50+5*(70-50)/(115-100)=56.7$ ,
- at time 110 min, BG reading= $50+10*(70-50)/(115-100)=63.3$

Glucose reading intervals  $>15$  minutes will be treated as missing data and not be counted in the length of the analysis periods.

For the primary analysis, CGM data must meet minimal completeness criteria for the period and the session in order to be included as a valid time period and session.

As shown in the table below, all the CGM derivations are based on the data from valid CGM periods of a day and sessions unless otherwise specified.

### Minimum Data Available to Define a Valid Period of the Day and CGM Session

Period	Definition	Minimum Valid CGM Time Period for a Session
Valid CGM Day (00:00-23:59)	$\geq 70\%$ of expected values available ( $\geq 202$ of 288 values)	3 valid CGM days define a CGM session for 24-hour

Valid CGM Nighttime (00:00-05:59)	$\geq 70\%$ of expected values available ( $\geq 50$ of 72 values)	3 valid CGM days define a CGM session for Nighttime
Valid CGM Daytime (06:00-23:59)	$\geq 70\%$ of expected values available (151 of 216 values)	3 valid CGM days define a CGM session for Daytime

Sensitivity analysis will be done for selected parameters including all CGM data.

The ambulatory glucose profile during the 24-hour period will be generated with interquartile ranges, at treatment-group level by CGM session, based upon the observed and imputed CGM measures.

### 6.6.1. Glucose in Target Ranges, Hypoglycemia or Hyperglycemia

The following variables of time in range, hypoglycemia, hyperglycemia during each CGM session will be derived:

- Percentage and Duration (in minutes) of time per day where glucose values are within a hypoglycemic range (defined as  $<54$  mg/dL [3.0 mmol/L]) during the nighttime period (defined as midnight to 0600 hours), the daytime period (defined as 0600 hours to 2400 hours) and a 24-hour period.
- Percentage and Duration (in minutes) of time per day where glucose values are within a hypoglycemic range (defined as  $<70$  mg/dL [3.9 mmol/L] and  $\geq 54$  mg/dL [3.0 mmol/L]) during the nighttime period, the daytime period, and a 24-hour period.
- Percentage and Duration (in minutes) of time per day where glucose values are within a hypoglycemic range (defined as  $<70$  mg/dL [3.9 mmol/L]) during the nighttime period, the daytime period and a 24-hour period.
- Percentage and Duration (in minutes) of time per day glucose values are within a hyperglycemic range (defined as  $>180$  mg/dL [10.0 mmol/L] and  $\leq 250$  mg/dL [13.9 mmol/L]) during the nighttime period, the daytime period and a 24-hour period.
- Percentage and Duration (in minutes) of time per day glucose values are within a hyperglycemic range (defined as  $>250$  mg/dL [13.9 mmol/L]) during the nighttime period, the daytime period and a 24-hour period.
- Percentage and Duration (in minutes) of time per day glucose values are within a hyperglycemic range (defined as  $>180$  mg/dL [10.0 mmol/L]) during the nighttime period, the daytime period and a 24-hour period.
- Percentage and Duration (in minutes) of time per day glucose values are within a glucose range (defined as between 70 mg/dL and 180 mg/dL [3.9 and 10.0 mmol/L]) inclusive during the nighttime period, the daytime period and a 24-hour period.
- Percentage and Duration (in minutes) of time per day glucose values are within a glucose range (defined as between 70 mg/dL and 140 mg/dL [3.9 and 7.8 mmol/L] inclusive) during the nighttime period, the daytime period and a 24-hour period.

The percentage of time within a glucose range (target, hypoglycemia, or hyperglycemia ranges) will be calculated as the number of observations within the specified range divided by the

number of observations in the time interval (for example, 24-hour period). The average percentage of time among valid CGM days for the corresponding time interval during each CGM session will be used in the analysis.

The duration (in minutes) within the glucose range will then be calculated as the average percentage of time within the glucose range times the length of the period (24-hour, 18-hour, and 6-hour, for the periods of 24-hour, daytime or nighttime, respectively).

According to the guidance (Battelino et al. 2019), the following CGM targets of glycemic control will also be derived during a 24-hour period.

- The percentage of time within a normal glucose range (defined as between 70 mg/dL and 180 mg/dL [3.9 and 10.0 mmol/L] inclusive) >70%
- The percentage of time within a hypoglycemia range (defined as <70 mg/dL [3.9 mmol/L]) <4%
- The percentage of time within a hypoglycemia range (defined as <54 mg/dL [3.0 mmol/L]) <1%
- The percentage of time within a hyperglycemic range (defined as >180 mg/dL [10.0 mmol/L]) <25%
- The percentage of time within a hyperglycemic range (defined as >250 mg/dL [13.9 mmol/L]) <5%

In addition, according to the guidance in 2023 (Battelino et al. 2023), 2 composite endpoints will be derived during a 24-hour period:

- >70% time in range 70 -180 mg/dL (3.9 - 10.0 mmol/L inclusive) and <4% time below range <70 mg/dL (<3.9 mmol/L)
- >70% time in range 70 -180 mg/dL (3.9 - 10.0 mmol/L inclusive) and <1% time below range <54 mg/dL (<3.0 mmol/L)

The daily duration (in minutes) of time within a glucose range (defined as <54 mg/dL [3.0 mmol/L]; <70 mg/dL [3.9 mmol/L] and  $\geq$ 54 mg/dL [3.0 mmol/L]; <70 mg/dL [3.9 mmol/L];  $\geq$ 70 mg/dL [3.9 mmol/L] and  $\leq$ =140 mg/dL [7.8 mmol/L];  $\geq$ =70 mg/dL [3.9 mmol/L] and  $\leq$ =180 mg/dL [10.0 mmol/L]; >180 mg/dL [10.0 mmol/L] and  $\leq$ =250 mg/dL [13.9 mmol/L]; >250 mg/dL [13.9 mmol/L]) will be merged with the dose administration data to get the summary of daily time in each glucose range since dose administration in each CGM session in the treatment period. For LY3209590, days relative to dose administration will be derived as 0 (dosing day), and then 1, 2, ..., up to 6 days after most recent dose administration but before the next dose administration. The average daily time in each glucose range for the given day (0 to 6) relative to the dose administration among valid CGM days (with at least 70% of the data of each day) during each CGM session will be used in the analysis.

### 6.6.2. Hypoglycemic Episode

According to the International Consensus Statement (Battelino et al, 2023), the CGM-determined hypoglycemic episodes for Level 1 or 2 and Level 2 are defined as below.

- Level 2 hypoglycemia (BGs<54 mg/dL)
  - Starting time: is the time of the 1st BG of BGs<54 mg/dL for >=15 consecutive min (regardless of number of BG readings)
  - Ending time: is the time of the last BG of the BGs>=54 mg/dL for 15 consecutive min (regardless of number of BG readings)
  - Duration: Time of the last BG <54 mg/dL – the time of the 1st BG<54 mg/dL
- Level 1 or 2 hypoglycemia (BGs<70 mg/dL)
  - Starting time: is the time of the 1st BG of BGs<70 mg/dL for >=15 consecutive min (regardless of number of BG readings)
  - Ending time: is the time of the last BG of the BGs>=70 mg/dL for 15 consecutive min (regardless of number of BG readings)
  - Duration: Time of the last BG <70 mg/dL - the time of the 1st BG<70 mg/dL
- Level 2 hypoglycemia ending with BG >=70 mg/dL (start with BG<54mg/dL, end with BG>=70 mg/dL)
  - Starting time: is the time of the 1st BG of BGs<54 mg/dL for >=15 consecutive min (regardless of number of BG readings)
  - Ending time: is the time of the BG that ensures the BGs>=70 mg/dL for 15 consecutive min (regardless of number of BG readings)
  - Duration: Time of the last BG <70 mg/dL – the time of the 1st BG<54 mg/dL

If the truncated time interval is >7 and <=15 minutes, use linear interpolation to impute the missing data at 5-minute intervals as described in Section [6.6](#).

If the truncated time interval is >15 minutes

- at any time, which make the starting time undeterminable, then do not count this time interval and no episodes start.
- If it is after an episode started, which makes the ending time undeterminable, then the episode ends at the starting time of the truncation.
- If an episode started and continued until the end of a CGM session, then the episode ends at the end of CGM session.

The average duration, incidence, event rate of the Level 1 or 2 and Level 2 hypoglycemia episodes will be analyzed for each CGM session as planned in Section [4.6.2.2.2](#). The average duration will be calculated by dividing the sum of the duration of individual episodes during the given CGM session by the number of episodes and used in the analysis. The hypoglycemic event

rate (events/participant/year) will be calculated by dividing the number episodes by the number of CGM days  $\times$  365.25 days.

The duration (minute) for a day= the time of last CGM value - the time of the 1st CGM value - the sum of intervals that are  $>15$  minutes within each CGM day.

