#### 4.6.2.2.2. Hypoglycemic Events derived from CGM

Level 2, Level 2 ending with BG value  $\geq 70$  mg/dL, and Level 1 or Level 2 hypoglycemic events collected from the sponsor provided CGM are defined in Appendix 6, Section 6.6.2. The analysis for incidence, event rate, and duration are described in the table below. All data are included in the analysis. Missing data will be handled as described in Appendix 6.

Endpoint	CGM Session*	Statistical Method
Event rate of Level 1 or Level 2 hypoglycemic events (events/participant/year): 
 
• 24-hour
 
	Baseline, 0-4, 8-12, 22-26, 0-26 weeks, post-treatment period	Negative binomial regression with treatment, baseline HbA1c and baseline Level 1 or Level 2 hypoglycemia rate as covariates, log (exposure/365.25 days) as the offset in the model.
Event rate of Level 2 hypoglycemic events (events/participant/year): 
 
• 24-hour
 
	Baseline, 0-4, 8-12, 22-26, 0-26 weeks, post-treatment period	Negative binomial regression with treatment, baseline HbA1c and baseline Level 2 hypoglycemia rate as covariates, log (exposure/365.25 days) as the offset in the model.

Endpoint	CGM Session*	Statistical Method
Event rate of Level 2 hypoglycemic events ending with $\geq 70$ mg/dL (events/participant/year): • 24-hour	Baseline, 0-4, 8-12, 22-26, 0-26 weeks, post-treatment period	Negative binomial regression with treatment, baseline HbA1c and baseline rate for Level 2 hypoglycemia ending with $\geq 70$ mg/dL as covariates, log (exposure/365.25 days) as the offset in the model.
Incidence of Level 1 or Level 2 hypoglycemic events: • 24-hour	Baseline, 0-4, 8-12, 22-26, 0-26 weeks, post-treatment period	Logistic regression with treatment, baseline HbA1c and baseline Level 1 or Level 2 hypoglycemia rate as covariates.  The total number of episodes, number of episodes that includes Level 2 hypoglycemia episodes, and number of episodes that include glucose readings $<54$ mg/dL(3.0 mmol/L) but no Level 2 hypoglycemia episodes will be summarized for each CGM session.
Incidence of Level 2 hypoglycemic events: • 24-hour	Baseline, 0-4, 8-12, 22-26, 0-26 weeks, post-treatment period	Logistic regression with treatment, baseline HbA1c and baseline Level 2 hypoglycemia incidence as covariates.

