Incidence of Level 2 hypoglycemic events ending with $\geq 70$ mg/dL: • 24-hour	Baseline, 0-4, 8-12, 22-26, 0-26 weeks, post-treatment period	Logistic regression with treatment, baseline HbA1c and baseline incidence for Level 2 hypoglycemia ending with $\geq 70$ mg/dL as covariates.

Endpoint	CGM Session*	Statistical Method
Duration of Level 1 or Level 2 hypoglycemic events: 
 
• 24-hour
 
	Baseline, 0-4, 8-12, 22-26, 0-26 weeks, post-treatment period	For 0-4, 8-12, 22-26 weeks: The MMRM model will include treatment, strata (country, routine use of personal CGM or FGM at randomization, baseline HbA1c stratum (<8.0%, ≥8.0%)), time and treatment-by-time interaction as fixed effects, and baseline duration as a covariate. For 0-26 weeks: ANCOVA model model will include treatment, strata (country, routine use of personal CGM or FGM at randomization, baseline HbA1c stratum (<8.0%, ≥8.0%)), and baseline duration. For Baseline and post-treatment period: ANOVA models only include treatment.
Duration of Level 2 hypoglycemic events: 
 
• 24-hour
 
	Baseline, 0-4, 8-12, 22-26, 0-26 weeks, post-treatment period.	Same models as for Level 1 or Level 2 hypoglycemic events. A listing will be provided for participants with Level 2 hypoglycemia episodes lasting >360 minutes
Duration of Level 2 hypoglycemic events ending with BG >=70 mg/dL: 
 
• 24-hour
 
	Baseline, 0-4, 8-12, 22-26, 0-26 weeks, post-treatment period.	Same models as for Level 1 or Level 2 hypoglycemic events.

Abbreviations: HbA1c = hemoglobin A1c.

Note: The hypoglycemic rate during defined period is a yearly rate and calculated by number of hypoglycemic events within the period/number of days patient at risk within the period\*365.25. The hypoglycemia incidence during defined period indicates if the patient has at least 1 hypoglycemic event within the period (Yes/No).

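### CGM episode duration has no value when a participant has no baseline episode, yet baseline duration is a covariate in the on-treatment duration models

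*SAP*

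**What the plan says.** - **Outcome.** SAP Section 6.6.2 derives average duration for each CGM session by "dividing the sum of the duration of individual episodes during the given CGM session by the number of episodes", and uses that figure in the analysis.
- **Treatment-period models.** SAP Section 4.6.2.2.2 fits an MMRM for Weeks 0-4, 8-12 and 22-26 with treatment, strata, "time and treatment-by-time interaction as fixed effects, and baseline duration as a covariate". The ANCOVA for Weeks 0-26 also includes baseline duration.
- **Other periods.** For the baseline and post-treatment periods, "ANOVA models only include treatment".
- **Episode definitions.** The models are written out for Level 1 or Level 2 episodes. Both Level 2 rows (the plain definition, and the one that ends at 70 mg/dL or above) say "Same models as for Level 1 or Level 2 hypoglycemic events".
- **Missing data.** The section opens with "All data are included in the analysis. Missing data will be handled as described in Appendix 6". Appendix 6 (Section 6.6) deals with gaps in the glucose trace: "Linear interpolation will be used to impute the missing glucose readings during intervals" of more than 7 and up to 15 minutes, with separate rules for longer gaps, truncated episodes and valid days. It gives no value for a session in which no episode occurred.
- **Baseline window.** Baseline CGM is worn for two weeks of lead-in (Section 6.6). The protocol's visit-interval rule allows 11 to 17 days between Visits 2 and 3.

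**The concern.** Minutes per episode exists only for someone who had an episode. A participant who wore the sensor throughout the lead-in without one does not have an unobserved baseline duration; the quantity is undefined. A regression does not use a record whose covariate is missing, so every on-treatment episode of that participant drops out of the model, however many there are and however long they last.

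Coding the missing value as 0 would keep the record, but it places no episode on the same scale as an episode of zero minutes and forces one slope through both. The SAP does not say which applies, so the analyzed population depends on an unstated programming choice.

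The neighboring analyses do not have this problem. The CGM rate and incidence models adjust for baseline rate or incidence, which is 0 or no when nothing happened.

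The stake is how many participants inform the comparison of episode length, and which ones. Those lost are participants whose episodes appear on treatment after an episode-free lead-in. The protocol lists hypoglycemia among the potential risks (Section 2.3.1) and puts the half-life of LY3209590 at about 17 days (Section 6.6.1), so episode length is worth estimating well.

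**Working it through.** **Is there a rule elsewhere?** The only baseline imputation for CGM data is in SAP Section 4.4.2.1. It belongs to the treatment regimen estimand for efficacy endpoints. Section 4.4.2.2 sends CGM safety measures to 4.6.2.2.2, which points to Appendix 6. None of these covers a zero-episode session.

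**Is there a figure to reproduce?** No. Neither document states a CGM episode rate or an expected number analyzed. The only hypoglycemia rates given (SAP Section 5: 0.55 and 1.1 per participant-year) are for participant-reported nocturnal events; 1.1 serves here only as a low anchor.

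**Inputs.** From the documents: baseline 14 days, on-treatment session 28 days, 568 completers. Assumed: yearly episode rate m; gamma-Poisson counts with dispersion k (the shape is 1/k); and the same rate for each participant before and on treatment.

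**Formulas.**

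P0(d) = (1 + k·m·d/365.25)^(-1/k)

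Share lost = [P0(14) - P0(42)] / [1 - P0(28)]

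The numerator is the chance of no baseline episode and at least one in the session. The denominator is the chance of at least one in the session.

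**Worked case, m = 12, k = 1.** P0(14) = 0.6850, P0(42) = 0.4202, 1 - P0(28) = 0.4791. Share lost = 0.2648/0.4791 = 55%. Of 568 participants, 0.4791 × 568 = 272 have a session episode and 0.2648 × 568 = 150 of them have no covariate value.

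**Level 2 at modest rates:**

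| Episodes per year | Lost, shape 1 | Lost, shape 0.3 |
|---|---|---|
| 3 | 82% | 72% |
| 6 | 70% | 59% |
| 12 | 55% | 47% |
| 24 | 39% | 36% |

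Across these cases 9-48% of participants have a baseline episode.

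**Wider range, k from 0.5 to 4:**

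| Episodes per year | Lost | Number of 568 |
|---|---|---|
| 1.1 | 84-94% | 34-42 |
| 5 | 61-78% | 71-130 |
| 20 | 37-45% | 82-174 |
| 80 | 13-22% | 69-84 |
| 150-200 (frequent Level 1 or 2) | 4-17% | 21-65 |

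**Sensitivity.** With an 11- or 17-day baseline the range over 1.1-80 per year is 10-95%. For Weeks 0-26 (three sessions, 84 days) it is 15-94%.

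**Check on simulated data.** One data set of 568 participants at 10 episodes per year with k = 2 had 201 with a defined on-treatment duration. The ANCOVA as written used 102 of them, a loss of 99/201 = 49%; the formula gives (0.7524 - 0.5505)/0.3717 = 54%. With baseline duration set to 0 plus an any-baseline-episode indicator, all 201 were used.

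**The case against.** **The rule may exist elsewhere.** The SAP never says that an episode-free baseline is set to missing, and SAP Section 1 places dataset specifications in separate documents. This stands in part: the loss follows only if 0/0 is left missing. But the rule decides who is analyzed, so it belongs in the SAP, and coding 0 alone brings its own distortion.

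**The size rests on assumed rates.** This stands. A reader might infer from the Level 2 figures that most participants are lost in every row. The documents cannot show that, and for frequent Level 1 or 2 episodes the loss may be only a few percent.

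**Bias.** A reader might infer that the exclusion tilts the comparison between arms. It depends only on pre-randomization data, so it does not itself unbalance them. A separate selection is post-randomization: the outcome exists only for participants with an on-treatment episode. No choice of baseline covariate removes that.

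**Contradiction.** A reader might set the loss against the sentence that all data are included. That sentence can equally mean that the valid-day and valid-session filter of Section 6.6 is not applied to episode analyses. It is not clearly a promise that everyone enters every regression.

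**Unseen events.** A reader might infer that new or prolonged episodes go unreported. They do not. The CGM incidence and rate models keep these participants, as do the analyses of time below 54 mg/dL (an other secondary endpoint). Level 2 episodes over 360 minutes are listed with no baseline condition. The post-treatment duration model has no covariate.

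**Conclusion.** The gap is real: the on-treatment duration models adjust for a quantity that does not exist for participants without a baseline episode, and the SAP has no rule for them. If the value is left missing, those participants leave the model.

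The size is conditional on the assumed rates, the gamma-Poisson form and equal rates before and on treatment. It is about 36-82% of participants with a Level 2 episode in a four-week session at 3-24 episodes per year, 13-22% at 80 per year, and 4-17% for Level 1 or 2 at 150-200 per year.

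The consequence is lost precision and a result that generalizes less well. Per-episode duration is not a listed endpoint and lies outside the multiplicity-controlled tests, so the primary and key secondary conclusions are untouched.

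**What to change.** In the treatment-period duration models of SAP Section 4.6.2.2.2, replace baseline duration with a covariate defined for everyone with valid baseline CGM. Section 6.6.1 already derives suitable ones: baseline percent time below 54 mg/dL for the two Level 2 rows, and below 70 mg/dL for the Level 1 or 2 row. Baseline duration set to 0 together with an any-baseline-episode indicator would serve the same purpose, because the indicator separates no episode from a short one.

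Also label the per-episode mean as conditional on having an on-treatment episode, and present it beside the minutes per day in range already planned, which are 0 when there are none.

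The cost is a few lines of SAP text and one covariate change, with no new data. The small downside is that percent time may correlate less with per-episode duration than baseline duration does where both exist.
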